Investigational Protocol

Proposed Title: “PADRES” (Prior Axitinib as a Determinant of Outcome of REnal Surgery)

Co-Principal Investigators: [name].¹
UCSD Moores Cancer Center
[name]
Mail Code: 0987
[name]
[contact]
[contact]
Email: [contact]

[name].
Cleveland Clinic Taussig Cancer Center
[name]
[name]
[contact]
[contact]
E-mail: [contact]

[name], PhD
Section of Urologic Oncology
Glickman Urological and Kidney Institute
[name]
[name]
[contact]
[contact]
[contact]

Co-Investigators:

[name]	(UCSD)
J. [name]	(UCSD)
[name]	(UCSD)
[name]	(UCSD)
[name]	(Cleveland Clinic)
[name]	(Cleveland Clinic)
[name], PhD	(Spectrum Health/Michigan State)
[name]	(Fox Chase Cancer Center)
[name]	(Netherlands Cancer Institute)
[name]	(MD Anderson)
[name]	(MD Anderson)
[name]	(UT Southwestern)
[name]	(Mayo Clinic)
[name]	(Mayo Clinic)

[name] (U Wisconsin)
[name] (NYU)
[name] (NYU)
[name] (Vanderbilt)
[name] (KU Leuven)
[name] (KU Leuven)

Statistician: [name], MS
Clinical and Translational Research Institute
UC San Diego Health
[name]
[name]
[contact]
Email: [contact]

Research Coordinator: [name], CCRC
Clinical Research Coordinator
UC San Diego Moores Cancer Center
Clinical Trials Office, Rm # 2011
[name]
[name]
[contact]
[contact]
[contact]
Email: [contact]

Responsible Data Manager: [name], MS
Database Program Manager
UC San Diego Health System-Department of Urology
[name]
Moores Cancer Center Office: 2032
[name]
[contact]
[contact]
Email: [contact]

Investigational Agent: Axitinib

Sponsor: University of California San Diego

Protocol Version Date: May 31, 2017

SCHEMA

A single arm phase II study of axitinib in patients with clear cell renal cell carcinoma (RCC) in patients with strong indications for partial nephrectomy (PN) for whom PN is not currently possible due to anatomic considerations and residual renal function concerns. Evaluation of tumor downsizing will be performed including changes of tumor complexity by nephrometry score (n=50 total).

Evaluation:

- 1) Cross Sectional Imaging (CT a/p, or MRI as indicated) to delineate renal mass and surrounding structures:

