4.3 Duration of Therapy

Treatment may continue until one of the following criteria applies:

- A total of 8-10 weeks of axitinib therapy (at which point partial/radical nephrectomy would be undertaken at the discretion of the operating surgeon). A decision regarding nephrectomy will be made at re-staging done at week 8 of therapy.
- Disease progression, as defined by RECIST criteria, v1.1,
- Intercurrent illness that prevents further administration of treatment,
- Unacceptable adverse event(s)
- Patient decides to withdraw from the study, or
- General or specific changes in the patient's condition render the patient unacceptable for

further treatment in the judgment of the investigator.

- If axitinib treatment is unsuccessful (i.e. is unable to render a large and complex mass for a partial nephrectomy), radical nephrectomy would be offered. The large size of the masses will mean that they are of significant risk oncologically to the patient and as such would not be candidates for an alternative approach such as radiofrequency or cryoablation (utilized when tumors are less than <3.5 cm in size) or active surveillance.

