10. STATISTICAL CONSIDERATIONS

Sample Size/Power Calculation:

Our sample size calculation is based on the data of Rini et al. (2015) who reported that 80% (20/25) of patients successfully underwent partial nephrectomy; from our institutional database the success rate was utilizing Sunitinib the success rate in imperative indications was 78.6% (11/14).

Assuming a true rate of successful intervention of 75%, a one proportion z-test will have 80% power (Beta 20%) at the two-sided 0.05 (alpha) significance level to detect a rate of success of at least 56.4%. To account for a potential dropout rate of 10%, we will have total sample size to 50 (Figure)

Statistical Analysis:

We will examine patients in whom the operation was feasible vs. those in which it was not. Summary statistics (mean, standard deviation, quintiles, counts, and percentages) and plots will be produced for all demographic (i.e. age, sex, race, BMI, Charlson score, etc), clinical disease characteristics (tumor size prior to treatment, RENAL score), surgical outcomes (margin status, estimated blood loss, transfusions) and complications, and renal functional outcomes (change in eGFR, decline in GFR >50% of preoperative value, and dialysis dependence). In comparing any of these measures between patient groups, we will use either Fisher's Exact test or the Chi-Squared test for categorical variables and a t-test for continuous variables. We will consider the use of the Mann-Whitney U-test as a robust alternative if the assumptions of the t-test are not met.

We will use a logistic regression to examine the impact of factors associated with complications / blood transfusions and GFR decline > 50%, and a linear regression to examine factors associated with changes in GFR. Standard model diagnostics will be assessed before any inference is derived. All statistical analysis will be conducted using the latest version of R (R Foundation for Statistical Computing, Vienna, Austria. <http://www.r-project.org/>).

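### The stated 80% power against 56.4% appears to rest on all 50 patients being analysed, so N = 50 seems to hold no reserve for the 10% dropout

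*Protocol*

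**What the plan says.** Section 10 (Statistical Considerations), under Sample Size/Power Calculation, starts from "Assuming a true rate of successful intervention of 75"%. It names a one-proportion z-test with "80% power (Beta 20%) at the two-sided 0.05 (alpha) significance level to detect a rate of success of at least 56.4"%. The next sentence sets the total: "To account for a potential dropout rate of 10%, we will have total sample size to 50", and points to a figure that is not reproduced in the text at hand. The Schema confirms 50 as the total.

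The text does not print the number of analysed patients behind the 80%. It does not label either rate as the null, and it does not name the variance form.

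On outcomes, Section 4.3 (Duration of Therapy) covers patients whose tumour cannot be made suitable for partial nephrectomy (PN): "radical nephrectomy would be offered". It lists patient withdrawal as a separate reason for ending treatment.

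**The concern.** A dropout allowance means that the power holds for the smaller number left after dropout. Here that is 45, since 50 × 0.90 = 45. If the 80% and the 56.4% were instead computed with 50 analysed, the allowance is stated but not built in, and the trial has less power than the protocol says.

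The allowance also leaves the denominator of the primary rate unclear. A patient who ends in radical nephrectomy has a known result: no PN. If such patients count as failures, no allowance is needed for them. If some treated patients are instead removed as dropouts, the reported rate shifts. For illustration, 34 successes are 68.0% of 50 (34/50) but 75.6% of 45 (34/45). In a single-arm trial whose main result is one proportion, that difference matters.

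**Working it through.** **Inputs.** From Section 10: true rate p1 = 0.75; comparison rate p0 = 0.564, read as the null; two-sided alpha 0.05 (z = 1.96); power 80% (z = 0.8416, so the sum is 2.8016); N = 50; dropout 10%. The analysed n is not printed, so 45 and 50 were both tried.

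**Step 1: which n reproduces the printed 56.4%?** The arcsine form gives the detectable null as sin²(asin√0.75 − 2.8016/(2√n)), with asin√0.75 = 1.0472.
- n = 50: sin²(1.0472 − 0.1981) = 0.5635, which rounds to the printed 56.4%.
- n = 49 gives 56.15% and n = 51 gives 56.55%.
- n = 45: sin²(1.0472 − 0.2088) = 0.5529.

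**Step 2: power at the printed rates.**
- Score form: Φ((0.186√n − 1.96√(0.564 × 0.436))/√(0.75 × 0.25)). At n = 45 this is Φ((1.2477 − 0.9719)/0.4330) = Φ(0.637) = 73.8%. At n = 50 it is Φ((1.3152 − 0.9719)/0.4330) = Φ(0.793) = 78.6%.
- Arcsine form: Φ((2asin√0.75 − 2asin√0.564)√n − 1.96) = Φ((2.0944 − 1.6991)√n − 1.96). This is Φ(0.691) = 75.5% at 45 and Φ(0.835) = 79.8% at 50.

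**Step 3: five usual forms side by side.** Role reversal means 75% as the null and 56.4% as the alternative, with the score form.

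| Form | Power, n = 45 | Power, n = 50 | Detectable rate, n = 45 | Detectable rate, n = 50 | n for 80% power |
|---|---|---|---|---|---|
| Arcsine | 75.5% | 79.8% | 55.3% | 56.35% | 50.2 |
| Score | 73.8% | 78.6% | 55.0% | 56.1% | 51.6 |
| Null variance only | 71.1% | 75.6% | 54.2% | 55.3% | 55.8 |
| Roles reversed | 79.0% | 82.7% | 56.1% | 57.1% | 46.3 |
| Variance at 75% only | 82.2% | 85.9% | 56.9% | 57.8% | 42.5 |

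Only one of these ten combinations returns 56.4%: arcsine at 50. None does so at 45.

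**Step 4: exact binomial enumeration.** With 45 analysed, the z-test rejects upward at 32 or more successes: power 78.4%, true two-sided alpha 0.051. An exact test that keeps alpha at or below 0.05 needs 33 or more: power 67.5%. With 50 analysed, both tests need 36 or more: power 74.8%, alpha 0.046.

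**Step 5: what if dropouts count as failures?** If 75% is the rate among evaluable patients and 10% drop out, the rate among all treated is 0.75 × 0.90 = 67.5%. Power at n = 50 against 56.4% is then 36.7% (arcsine), 34.5% (score) or 30.3% (exact, 36 or more).

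**The case against.** The strongest reply is that the analysed number has been worked out backwards, while the printed totals agree with each other: 45/0.9 is exactly 50. The missing figure may state the analysed number. The protocol names a z-test, not an arcsine calculation, and the score form at 50 gives 56.1%, not 56.4%. The reversed-role score form at 45 also gives 56.1%, with 79.0% power, and the wording "to detect a rate of success of at least 56.4"% does not rule that reading out. With variance at 75% only, 45 patients are more than enough. Exact enumeration of the z-test even gives higher power at 45 (78.4%) than at 50 (74.8%).

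Much of this stands, and it limits the claim. A reader might infer that the dropout was certainly left out of the calculation; the documents do not support that. Two points still favour 50. The protocol calls 75% the assumed true rate, which makes it the alternative and not the null. Neither rival form returns the printed 56.4% at 45. The exact result at 45 reflects the uneven steps of the binomial, with a true alpha slightly above 0.05, so it does not show that 45 is the better size.

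A second tempting reading is that the endpoint needs no dropout allowance at all. That goes too far. Section 4.3 lists withdrawal separately from unsuccessful treatment, and a patient who withdraws may have an unknown surgical outcome.

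**Conclusion.** The concern holds as a strong inference. With 75% as the true rate, 56.4% as the null and 45 patients analysed, power is 73.8% (score) to 75.5% (arcsine). That is about 4 to 6 points below the stated 80%. At 80% power the detectable null is about 55%, not 56.4%. The 80% appears to rest on all 50 patients.

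The size depends on the form: across the five forms, power at 45 runs from 71.1% to 82.2%. The 4 to 6 points assume the arcsine or score form with 75% as the alternative. The number of patients need not change. The stated power, and the denominator to which it applies, should be restated.

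**What to change.** Keep N = 50. In Section 10, state which rate is the null and which the alternative, name the formula, and print the analysed n. Then choose one of two routes.

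- **(a) Evaluable patients only.** Keep the 10% allowance and 45 analysed. Restate power as about 74% to 75.5% against 56.4%, or give the detectable null as about 55% at 80% power.
- **(b) All patients who start axitinib.** Count no PN, for any reason, as failure and drop the dropout allowance. State power for 50 as 79.8% (arcsine), 78.6% (score) or 74.8% (exact, 36 or more of 50), and report an evaluable-only rate as a sensitivity analysis. The text must say that 75% is the all-treated rate, dropouts included. The 20/25 benchmark in Section 10 suggests this, because Section 2.3.2 says that 25 patients were enrolled in that pazopanib study. If 75% is meant for evaluable patients only, these figures must not be printed, because power at 50 would then be about 30% to 37% (working, step 5).

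The cost is protocol wording only, with no extra patients. The downside is a slightly less favourable stated power and, under (b), possibly a lower reported success rate.

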11.0 DATA REPORTING AND MONITORING REQUIREMENTS

This monitoring committee will include the three senior co-investigators, [name], [name], and [name], PhD. The committee will convene electronically and by phone on a monthly basis to review safety and toxicity information.

If 10 out of the first 15 participants are not able to safely proceed to nephron sparing surgery, the study will be stopped.

Appendix 1: Axitinib Guidance Document: Concomitant Medication

Concomitant Medications and Non-Drug Therapies

Permitted Medications

All subjects will be asked to provide a complete list of prescription and over-the-counter medications that have been taken within the previous 4 weeks prior to Screening. The investigator must be informed as soon as possible about any new medication(s) taken from the time of Screening until the completion of the post-treatment follow-up visit.

All concomitant medications taken during the study will be recorded in the case report form (CRF) with indication, dose information, and dates of administration.

Subjects should receive full supportive care during the study, including transfusion of blood and blood products, treatment with antibiotics, analgesics, erythropoietin, or bisphosphonates, when appropriate.

Anti-emetics (such as prochlorperazine, lorazepam, ondansetron or other 5-HT antagonists) may be administered prophylactically in the event of nausea. Anti-diarrheals, such as loperamide, may be administered as needed in the event of diarrhea. Although acetaminophen at doses of ≤ 2 g/day is permitted, it should be used with caution in subjects with impaired liver function.

Permitted Medications – Use with Caution

Specific recommendations regarding anticoagulants:

Results from drug-drug interaction studies conducted in subjects with cancer suggest that pazopanib has no effect on the metabolism of S-warfarin. Hemorrhagic events, however, have been reported in clinical studies with tyrosine kinase inhibitors; therefore, axitinib should be used with caution in subjects with increased risk of severe bleeding or who are receiving concomitant anticoagulant therapy (e.g., warfarin or its derivatives, low molecular weight heparin, unfractionated heparin). Subjects taking concomitant anticoagulant therapy should be monitored regularly for changes in relevant coagulation parameters as clinically indicated, as well as for

any clinical bleeding episodes.

Specific recommendations regarding hypoglycemic therapy including insulin:

Results from drug-drug interaction studies conducted in subjects with cancer suggest that there will be no clinically relevant pharmacokinetic interaction between axitinib and hypoglycemic agents. Transient decreases in serum glucose (mainly Grade 1 and 2, rarely Grade 3) have been observed in clinical studies with pazopanib. In addition, decreases in blood sugar have been recently reported in subjects treated with sunitinib. Such changes may require an adjustment in the dose of hypoglycemic and/or insulin therapy. Subjects should be advised to report symptoms of hypoglycemia (e.g., confusion, visual disturbances, palpitations, sweating). Serum glucose should be tested during treatment with pazopanib as outlined in the protocol and as clinically indicated.

The Effects of Axitinib on Other Drugs^{1,2}

Axitinib is metabolized primarily in the liver by cytochrome P450 (CYP) 3A4/5 and, to a lesser extent (<10 % each), by CYP1A2, CYP2C19, and uridine diphosphate glucuronosyltransferase (UGT) 1A1. The two major human plasma metabolites, M12 (sulfoxide product) and M7 (glucuronide product), are considered pharmacologically inactive. Axitinib is eliminated via hepatobiliary excretion with negligible urinary excretion. Although mild hepatic impairment does not affect axitinib plasma exposures compared with subjects with normal hepatic function, there was a 2-fold increase in AUC from time zero to infinity (AUC_{∞}) following a single 5-mg dose in subjects with moderate hepatic impairment. In the presence of ketoconazole, a strong CYP3A4/5 inhibitor, axitinib C max and AUC_{∞} increased by 1.5- and 2-fold, respectively, whereas co-administration of rifampin, a strong CYP3A4/5 inducer, resulted in a 71 and 79 % decrease in the C max and AUC_{∞} , respectively. Axitinib does not inhibit CYP3A4/5, CYP1A2, CYP2C8, CYP2A6, CYP2C9, CYP2C19, CYP2D6, CYP2E1, or UGT1A1 at concentrations obtained with the clinical doses and is not expected to have major interactions with drugs that are metabolized by these enzymes.

In addition, the potential for drug interaction with such medications, although diminished, may persist after the last dose of axitinib even with its relatively short half-life (i.e., 2.5-6.1 hours); therefore, continue to exercise **CAUTION** for at least 1 day and up to 2 days after the last dose of axitinib when administering these medications. These medications include

(but are not limited to):

- Ergot derivatives: dihydroergotamine, ergonovine, ergotamine, methylergonovine (potential increased risk for developing ergot toxicity that includes severe vasospasm leading to peripheral as well as cerebral ischemia)
- Neuroleptics: pimozide (potential increased risk for QT interval prolongation, ventricular arrhythmia, and sudden death)
- Antiarrhythmics: caution should be exercised when utilizing bepridil, flecainide, lidocaine, mexiletine, amiodarone, quinidine, propafenone (in tyrosine kinase inhibitors as a class, potential increased risk for QT interval prolongation and Torsade de Pointes; nonetheless a study by Ruiz-Garcia et al. in *Cancer Chemother Pharmacol* in 2015 noted that in healthy volunteers with Axitinib concentrations exceeded the range observed in RCC patients, axitinib was not associated with clinically significant QTc prolongation)²
- Immune modulators: cyclosporine, tacrolimus, sirolimus (potential increased risk for nephrotoxicity and neurotoxicity)
- Miscellaneous: quetiapine, risperidone, clozapine, atomoxetine.

The Effects of Other Drugs on Axitinib

Results from *in vitro* studies suggest that the oxidative metabolism of pazopanib in human liver microsomes is mediated primarily by CYP3A4/5, with minor contributions from CYP1A2 and CYP2C19.³ Furthermore, *in vitro* data suggest that axitinib is an inhibitor for p-glycoprotein. Substances that induce or inhibit CYP3A4 may alter the pharmacologic effects of pazopanib and should be used with **CAUTION**.

Medications that inhibit CYP3A4 may result in increased plasma pazopanib concentrations. Co-administration of strong CYP3A4 inhibitors is prohibited (see Section on Prohibited Medications); therefore selection of an alternate concomitant medication with no or minimal potential to inhibit CYP3A4 is recommended.

CYP3A4 inducers may decrease plasma pazopanib concentrations. Selection of an alternate concomitant medication with no or minimal enzyme induction potential is recommended. **Drugs that induce CYP3A4 and may decrease axitinib plasma concentrations include (but are not**

limited to):

- Glucocorticoids: cortisone (>50 mg), hydrocortisone (>40 mg), prednisone (>10 mg), methylprednisolone (>8 mg), dexamethasone (>1.5 mg)
- Anticonvulsants: phenytoin, carbamazepine, phenobarbital, oxcarbazepine
- HIV antivirals: efavirenz, nevirapine
- Antibiotics: rifampin (rifampicin), rifabutin, rifapentene
- Miscellaneous: St. John's Wort, modafinil, pioglitazone, troglitazone

Prohibited Medications⁴

Subjects should not receive other anti-cancer therapy [cytotoxic, biologic, radiation, or hormonal (other than leuprolide or other GnRH agonists)] while on treatment in this study.

Medications that inhibit CYP3A4 and 1A2 inducers may result in increased plasma pazopanib concentrations; therefore, co-administration of strong CYP3A4 inhibitors is **PROHIBITED** beginning 14 days prior to the first dose of study drug until discontinuation from the study.

Strong CYP3A4 inhibitors include (but are not limited to):

- Antibiotics: clarithromycin, telithromycin, troleandomycin
- HIV: protease inhibitors (ritonavir, indinavir, saquinavir, nelfinavir, amprenavir, lopinavir)
- Antifungals: itraconazole, ketoconazole, voriconazole, fluconazole
- Antidepressants: nefazodone

References for Appendix:

